Eligible patients with metastatic renal cell and urothelial cancers must have at least two separate measurable sites of disease. Extent of metastatic disease is recorded by CT scanning or MRI. There are two cohorts of patients; patients with renal cell carcinoma and patients with urothelial cancers. Patients will be stratified into one of two cohorts (based on tumor type, renal cell carcinoma [cohort 1] or urothelial carcinoma [cohort 2]) and subsequently randomized to either immunotherapy without radiation (Arm A) or immunotherapy with radiation (Arm B).

In Arm A:

1. Patient with Renal Cell carcinoma will receive Nivolumab alone Days* 1, 15, 29, 43 and 57.
2. Patients with Urothelial cancer will receive either Nivolumab on Days* 1, 15, 29 43 and 57, or Atezolizumab or Pembrolizumab on Days* 1, 22, 43 and 64.

(* - infusions will have a \pm 3 days window to accommodate inevitable scheduling changes and holidays)

In Arm B:

1. Radiation is given to one lesion, 30 Gy in 3 fractions of 10 Gy each, over a one week interval (with a minimum of 36hrs between each fraction), conformally or by intensity modulated radiation treatment to maximally spare normal tissue. On the day of radiation (Day 1) immunotherapy is administered and repeated on the scheduled days. Patients will receive radiation on Day 1 and immunotherapy will be given \pm 24hr from Day 1.
2. Patient with Renal Cell carcinoma will receive Nivolumab alone Days* 1, 15, 29, 43 and 57.
3. Patients with Urothelial cancer will receive either Nivolumab alone on Days* 1, 15, 29,43 and 57 or Atezolizumab or Pembrolizumab on Days* 1, 22, 43 and 64.

(* - infusions will have a \pm 3 days window to accommodate inevitable scheduling changes and holidays)

Patients on both treatment arms will undergo re-imaging on Day 63 (\pm 7days), (Renal cell carcinoma patients should have received 5 doses; Urothelial Cancer patients should have received 3-4 doses) and every 9 weeks (\pm 7 days) for one year and every 12 weeks(\pm 7 days) thereafter.

1.10 7.0 Correlative studies

1.10.1.1 7.1 Evaluation of the cellular immune responses

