9.0 Study Therapy [Nivolumab]

9.1 Nivolumab

Nivolumab is a human monoclonal antibody that blocks the interaction between PD-1 and its ligands, PD-L1 and PD-L2. Nivolumab is an IgG4 kappa immunoglobulin that has a calculated molecular mass of 146 kDa. Binding of the PD-1 ligands, PD-L1 and PD-L2, to the PD-1 receptor found on T cells, inhibits T-cell proliferation and cytokine production. Upregulation of PD-1 ligands occurs in some tumors and signaling through this pathway can contribute to inhibition of active T-cell immune surveillance of tumors. Nivolumab is a human immunoglobulin G4 (IgG4) monoclonal antibody that binds to the PD-1 receptor and blocks its interaction with PD-L1 and PD-L2, releasing PD-1 pathway-mediated inhibition of the immune response, including the anti-tumor immune response. In syngeneic mouse tumor models, blocking PD-1 activity resulted in decreased tumor growth.

Patients with Renal cell carcinoma will receive Nivolumab intravenously at a flat dose of 240mg every two weeks. Infusions will be given over 60 minutes (not bolus or IV push).

In Arm A:

Patient with Renal Cell carcinoma will receive nivolumab alone Days* 1, 15, 29, 43 and 57.

(* - infusions will have a \pm 3 days window to accommodate inevitable scheduling changes and holidays)

In Arm B:

Radiation is given to one lesion, 30 Gy in 3 fractions of 10 Gy each, over one week interval (with a minimum of 36 hours between each fraction), conformally or by intensity modulated radiation treatment to maximally spare normal tissue.

On the day of radiation (Day 1) immunotherapy is administered and repeated on the scheduled days. Patients will receive radiation on Day 1 and immunotherapy will be given \pm 24hr from Day 1.

Patients on both treatment arms will undergo re-imaging on Day 63 (\pm 7 days) (after the first 5 doses of Nivolumab) and every 9 (\pm 7 days) weeks for one year and every 12 weeks (\pm 7 days) thereafter. The first dose will be administered on Day 1 (\pm 24hrs) and repeated on Days 15, 22, 43 and 57. Radiation will be delivered every other day (with a minimum of 36 hours between the fractions) preferably starting on a Monday. A dose of 10 Gy x 3 days will be tested.

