11.0 Radiation Therapy Guidelines

11.1 Planning

After a lesion to be treated with radiotherapy is identified, the site is imaged at the time of CT simulation. Contrast Media may be used during the CT simulation, as deemed necessary by the treating physician. CT scan thickness should be <0.5 cm through the tumor bed region. These images will be used in treatment planning in accordance with the dose specific constraints per the Task Group 101 of the American Association of Physicists in Medicine.

The clinical tumor volume (CTV) is defined as the lesion of interest with the expected motion changes. The planning target volume (PTV) is the CTV + a 0.5-1 cm margin for setup error.

Respiratory gating may be used during the CT simulation to delineate an internal target volume (ITV) for chest and abdominal lesions that are subject to motion during the respiratory cycle. In this setting, a 0.5-1cm margin for setup error will be added to the ITV to establish the PTV.

Treatment Planning: 3D-Conformal or Intensity Modulated Radiation Therapy (IMRT) treatment planning is allowed. This includes “field-in-field” beams as well as the use of dynamic multi-leaf collimator (MLC) derived using inverse planning or electronic compensator techniques. Field arrangements and technique should be chosen that satisfy the PTV_{eval} and normal tissue dose constraints (TG101) using Dose-Volume Histogram (DVH) analysis by carefully selecting the gantry and table angle combinations that do not enter or exit through other organs of the body, the dose can be confined to the traditional treatment volumes. Non-coplanar beam arrangements are encouraged, but not required. Dose calculations with tissue inhomogeneity correction must be used. Beams entering lesions that will be monitored for abscopal responses will be avoided.

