The system provides audit trails that track creation and modification of records that include user ID and timestamp. Once entered, the data is subjected to validation procedures that are executed either immediately or upon saving the eCRF page or during the batch validation process. Validation failures that are identified before the page is saved can be corrected immediately. Validation failures during saving of the eCRF page and during batch validation processes will generate a discrepancy. Depending on the database account privileges, the data managers may be able to correct a discrepancy or if not, route it to the project data manager at WCM who can take appropriate action to correct the problem. Data clarification forms can also be printed out when necessary to be sent to the project data manager. Once the discrepancy is closed, by marking “resolved” or “irresolvable”, the data is marked clean and an audit trail is generated by the system.

All key end points will be source verified by a second person and errors will be corrected. Once the data is verified and all discrepancies are closed, the data can be locked/frozen. Locking and freezing can be done at different granular levels and will follow institutional SOPs and any specific requirements for the project.

Security measures that will be taken in order to protect patient data will include firewall technology and database level security which will be achieved by assigning roles and privileges to different levels of users and by requiring that the users authenticate themselves using user ID and password. Additional security for data transfer between remote clients and servers will be achieved by using digital certificates/SSL. All data will be backed-up to tape periodically according to the Institutional SOPs. All data will be stored for at least 5 years following the termination of this study.

1.24 29.0 Statistical Considerations

112 patients will be randomly assigned in a 1:1 ratio to treatment with immunotherapy (Nivolumab or Atezolizumab) or to treatment with immunotherapy (Nivolumab or Atezolizumab) plus radiotherapy in this phase II trial. With 56 patients per group, if the expected response rate (PR or CR) is 20% with immunotherapy alone, we can detect a response rate of 40% for immunotherapy plus radiotherapy with a 1-sided alpha of 20% and a power of 90%.

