Forty patients per year will be randomized to the trial over ~ 3 years of accrual, assuming an accrual rate of approximately 20 patients per year for each cohort (see study calendar).

1.24.1.1 29.1 Statistical analysis

Both arms will run in parallel but will be analyzed separately. When the target accrual is met for a cohort, it will be closed to accrual even though other cohorts may still be accruing. Analyses will be done separately for each arm. Analyses will be similar for the two arms.

The primary objective of this study is the comparison of best overall response rates between each arm after start of treatment. Fisher's Exact test will be used to estimate 95% confidence intervals for the difference and to perform a one-sided test with an alpha level of 20%. Response rates for each arm will also be estimated at this level. With 56 patients treated under each modality, if the true responses are 20% and 40% in the immunotherapy alone and immunotherapy and radiation arms, respectively, we have a 90% probability of detecting a difference between modalities. Secondary objectives include time to disease progression and mortality. Median times for these events will be estimated with 95% confidence intervals. Graphical summaries will include Kaplan-Meier curves and log-rank tests which will be used to detect differences between treatments. Median survival and progression times will be estimated if sufficient events are observed. Cox proportional hazards regression will be used to account for baseline characteristics. Stratified exploratory analyses by type of cancer (renal cancer cell carcinoma or urothelial carcinoma) will also be performed.

Toxicities will be summarized per arm and prepared using Chi-square or Fisher's Exact tests, where appropriate.

Patient and disease characteristics will be summarized and compared at randomization between the two treatment arms using descriptive statistics and graphical displays. Although randomization will remove systematic biases we will test for differences in arms using Chi-square or Fisher's exact methods for categorical variables and t-tests or Kruskal-Wallis tests (with appropriate transformations of data if necessary for continuous variables). Differences in RECIST outcomes within each patient comparing non-irradiated and irradiated lesions will be summarized. Similar techniques will be used for exploratory analyses of the following:

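### Scans are timed from Day 1 rather than randomisation, and the PFS origin is undefined, so a later start in Arm B would distort the PFS comparison in a direction that depends on the origin chosen

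*Combined protocol and SAP*

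**What the plan says.** Protocol section 6.2: "Patients on both treatment arms will undergo re-imaging on Day 63", with a window of 7 days either side, then every 9 weeks for one year and every 12 weeks after that. The day numbers are the same in both arms.

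They count from Day 1. For Arm B, section 6.2 says "On the day of radiation (Day 1) immunotherapy is administered and repeated on the scheduled days". In Arm A, Day 1 is the first infusion.

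Section 11.1 describes what precedes radiation: "After a lesion to be treated with radiotherapy is identified, the site is imaged at the time of CT simulation", followed by treatment planning. Arm A has no such step. No section gives a usual or maximum interval from randomisation to Day 1 in either arm. The nearest limit is in section 17.4.2, where baseline imaging may be at most 4 weeks old when treatment begins.

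Section 9.1 adds in parentheses, beside the Day 63 window, that the scan comes "after the first 5 doses of Nivolumab". Section 10.1 does the same with four doses of atezolizumab, although the fourth dose is scheduled for Day 64. Section 6.2 states only how many doses patients should have had by then.

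Section 29.1 plans Kaplan-Meier curves and "log-rank tests which will be used to detect differences between treatments" for progression and mortality. It gives no time origin and no alpha level for these tests. The only stated origin is start of treatment, and it concerns response (sections 18.3 and 29.1).

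**The concern.** Progression is mostly recorded at the first scan after it occurs, so the recorded date depends on the scan clock as well as on the disease. Here that clock starts at an event after randomisation, and one arm has an extra step before it.

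If Arm B patients reach Day 1 later, two things can happen. With PFS timed from randomisation, every Arm B scan falls later than its Arm A counterpart, and so does every scan-detected progression. With PFS timed from Day 1, the scans line up, but Arm B patients have had longer to progress before their clock starts. Either way, two arms with identical disease would show different PFS curves. Because the origin is undefined, the direction of the distortion stays open until someone chooses it at analysis.

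At stake is a secondary comparison that readers will use to judge whether radiotherapy delays progression.

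**Working it through.** **1. The plan's own figure.** The only power statement concerns response: "112 patients will be randomly assigned in a 1:1 ratio" (56 per arm), "if the expected response rate (PR or CR) is 20% with immunotherapy alone", "we can detect a response rate of 40% for immunotherapy plus radiotherapy", one-sided alpha 0.20, power 90%.

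- n = [z(0.20)·√(2·0.3·0.7) + z(0.10)·√(0.2·0.8 + 0.4·0.6)]² / 0.2² = (0.8416·0.6481 + 1.2816·0.6325)² / 0.04 = 45.96, so 46 per arm.
- With continuity correction: (45.96/4)·[1 + √(1 + 4/(45.96·0.2))]² = 55.5, so 56 per arm.
- Exact one-sided Fisher power at 56 per arm is 0.902.

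The figure is reproduced. It does not involve scan timing. No median, event count or power is stated for PFS.

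**2. The mechanism, by hand.** Assume an exponential median PFS of 3 months (91.3 days), so the hazard is 0.693/91.3 = 0.00759 per day in both arms. Assume Arm A starts 7 days after randomisation and Arm B 21 days after. The Day 63 scan then falls 70 days after randomisation in Arm A and 84 days after in Arm B.

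- From randomisation: at day 70, Arm A records 1 − exp(−0.00759·70) = 41% progressed. Arm B records none until day 84. This favours Arm B.
- From Day 1: both arms are scanned at day 63, but 41% of Arm A and 1 − exp(−0.00759·84) = 47% of Arm B have progressed. This counts against Arm B.

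**3. Simulation with no treatment effect.** From the documents: 56 per arm; scans every 63 days to day 378 and then every 84 days, ±7 days; log-rank test. Assumed: exponential progression, all of it found at scans; a 7-day start in Arm A; an extra Arm B lag as shown. There were 1,500 runs per cell. An HR below 1 favours Arm B. The rejection columns give the proportion of runs declaring Arm B better.

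| Median PFS | Extra lag (days) | HR, from randomisation | Rejection at 0.20 / 0.025 | HR, from Day 1 | Rejection at 0.20 |
|---|---|---|---|---|---|
| 3 months | 0 | 0.996 | 0.210 / 0.015 | 1.006 | 0.194 |
| 3 months | 7 | 0.852 | 0.469 / 0.146 | 1.041 | 0.140 |
| 3 months | 14 | 0.814 | 0.567 / 0.184 | 1.091 | 0.101 |
| 3 months | 21 | 0.843 | 0.503 / 0.139 | 1.133 | 0.073 |
| 5 months | 0 | 0.997 | 0.204 / 0.033 | 0.999 | 0.198 |
| 5 months | 7 | 0.916 | 0.347 / 0.076 | 1.028 | 0.162 |
| 5 months | 14 | 0.895 | 0.391 / 0.083 | 1.062 | 0.123 |
| 5 months | 21 | 0.914 | 0.356 / 0.077 | 1.082 | 0.113 |

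The simulation error is about √(0.2·0.8/1500) = 0.010 at the 0.20 level and √(0.025·0.975/1500) = 0.004 at 0.025. The plan sets no alpha for PFS: 0.20 is borrowed from the primary test and 0.025 is conventional.

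**4. A milder setting.** Some events are deaths with exact dates, which dilutes the effect. With 15% of events dated exactly, Arm A starting 2 days after randomisation and Arm B 9 or 16 days after, PFS from randomisation gives an HR of 0.88 at a 3-month median, 0.91 to 0.93 at 4 months and 0.95 at 6 months. Rejection at 0.025 is about 10%, 5 to 8% and 5%. Allowing for variation between simulations, lags of 1 to 2 weeks and medians of 3 to 6 months give an HR of about 0.87 to 0.95 with 4.5 to 11% rejection from randomisation, and an HR of about 1.02 to 1.11 from Day 1.

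**5. Dose holds.** A 14-day hold would move the fifth nivolumab dose from Day 57 to Day 71, beyond the Day 56 to 70 scan window. The dose count and the calendar would then disagree. If such holds did move scans, holds in 20% of both arms give an HR of 1.01, 10% against 20% gives 0.99, and 10% against 30% gives 0.95 to 0.98.

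**6. After the change.** With scans on the same days from randomisation in both arms, the zero-lag rows apply: HR 0.996 and 0.997, rejection at 0.20 of 0.210 and 0.204.

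**The case against.** The strongest reply is that the lag is assumed. The documents give no randomisation-to-Day-1 interval, an efficient clinic might start both arms together, and the 4-week limit on baseline imaging indirectly caps any delay. That stands: with no difference in start, there is no distortion.

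It can also be said that the documents lean towards start of treatment as origin, which aligns the scans. That removes the advantage to Arm B but does not rescue the comparison. It starts the clock at a post-randomisation time that may differ by arm, and the shift then runs the other way.

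A reader might infer that the plan favours radiotherapy on PFS. The documents do not support this, because that direction requires an origin they do not state. A reader might also infer that dose holds push Arm B scans later. That is not supported either. The dose counts are parentheses beside a calendar window, the calendars in sections 15.0 and 16.0 show a separate Day 63 column, and toxicity holds apply to both arms (section 27.2). Section 11.3 adds a delay rule for radiation toxicity, but nothing shows more holds in Arm B. With 25% of Arm B scans put back two weeks, false rejection was only 3 to 4% against a nominal 2.5%. With 1,000 runs the simulation error is about 0.5 points, so that is close to noise.

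Finally, the secondary objective is to estimate PFS, and no decision rule hangs on the log-rank test. That limits the importance of the point without removing it.

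**Conclusion.** The point holds as a conditional weakness in a secondary endpoint. Scans run from Day 1, PFS has no defined origin, and only Arm B has a planning step before Day 1. If that step delays Arm B by 1 to 2 weeks, PFS is distorted under no effect: HR about 0.87 to 0.95 from randomisation, or a modest shift the other way, about 1.02 to 1.11, from Day 1. If every progression were found only at scans, the shift from randomisation would be larger, 0.81 to 0.92 for the same lags.

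These sizes rest on assumed lags, assumed medians of 3 to 6 months and exponential progression. None of these is in the documents.

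It would go too far to conclude that the trial's main result is compromised. Best overall response over 96 weeks and its 90% power are not shown to be affected. The change is worth making because it is cheap and removes the dependence on start date.

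**What to change.** In sections 6.2, 9.1 and 10.1 and the calendars, schedule tumour assessments in both arms by calendar from the date of randomisation: every 9 weeks in year 1, then every 12 weeks, ±7 days, regardless of when treatment starts or how many doses have been given. In section 29.1, define PFS and OS from randomisation.

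Reconcile the dose counts in sections 9.1 and 10.1 with the calendar so that they cannot be read as scan triggers. The lists of infusion days within 6.2, 9.1 and 10.1 also disagree with one another and must be reconciled.

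Report the randomisation-to-Day-1 interval by arm. If the scans are already done, fix the origin before analysis and add an interval-censored PFS sensitivity analysis, placing each progression between the last scan without it and the first scan showing it.

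The cost is amendment wording, with no extra scans. The first Arm B scan would follow slightly less treatment time, and the CT could fall some days apart from the Day 63 visit and optional biopsy, which stay on the Day 1 clock.

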1.7 Summary of investigational program

1.8 5.0 Overall Risk/Benefit Assessment

Nivolumab, Atezolizumab and Pembrolizumab have demonstrated durable tumor regressions and upon use as single agents have generally been well tolerated in the majority of patients. Drug-related immune-mediated phenomena have been observed in about half of the patients, predominately involving the lung, GI

tract, endocrine glands, or skin. Serious drug related pneumonitis (defined as those meeting the SAE definition) occurred in approximately 1-2% of subjects. Treatment related pneumonitis causing death occurred in ~0.2% of patients. The rate of SAEs is less than would be expected with high dose IL-2 or combination chemotherapy regimens. Meanwhile, the expected response rate for PD1/PDL1 checkpoint blockade is in the 15 - 20% range. In addition, preliminary data suggest that duration of response with PD1/PDL1 checkpoint blockade may be more durable than responses with combination chemotherapy.

The overall risk benefit ratio for patients entering this protocol is therefore at least comparable to, and possibly better than alternative options.

1.9 6.0 Study Rationale

1.9.1.1 6.1 Combining radiotherapy and PD1/PDL1 blockade

The availability of Nivolumab and Atezolizumab and the Phase I/ II experience with the antibody, make them compelling to translate the preclinical findings of abscopal effects in poorly immunogenic syngeneic murine tumors. Moreover, modern image guided radiotherapy has the advantage of enabling conformal and precise delivery of large radiation doses to a selected volume, with both the advantage of convenience to the patient (only five visits) and possibly, the induction of a more favorable inflammatory response.

1.9.1.2 6.2 Study Design

The specific aims are:

1. To explore the induction of immune-mediated tumor responses outside the radiation field (abscopal effect) after immunotherapy and radiotherapy in metastatic renal cell and urothelial cancers, by estimating and comparing the best overall response (time frame: 96 weeks) rates in patients treated with immunotherapy alone or in combination with radiation.
2. To assess progression free survival (PFS), Overall survival (OS) and safety.
3. To compare the induction of effector T cell responses in patients with metastatic renal cell and urothelial cancer treated with either immunotherapy alone or in combination with radiation.

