The development of immune responses to multiple tumor associated antigens has been suggested to play a crucial role in determining the therapeutic efficacy of immunotherapy.³⁶ It has been suggested that the mutational load may predict for responses to PD1/PDL1 axis blockade and may be responsible for the expression of neoepitopes necessary for the development of antitumor immunity. These immune analyses are considered exploratory and ancillary to the primary goals of the trial. The most comprehensive analysis will be based on testing the T cell and B cell response to renal cell and urothelial cancer associated tumor antigens. The advantage of this approach is the inclusion of all antigens expressed by tumors including unknown as well as cryptic epitopes.

1.10.1.2 7.2 Immune monitoring

Serial blood samples collected at baseline, and at selected time points during and post treatment will be processed to collect plasma/serum and peripheral blood mononuclear cells (PBMCs) which will be used to evaluate humoral and cellular immunity induced by PD1/PDL1 axis blockade alone vs. PD1/PDL1 axis blockade and radiotherapy.

Immune monitoring labs will be collected before each infusion on the following days.

Nivolumab patients will have immune monitoring samples on Days 1(\pm 24hrs), 29 (\pm 3days), and 57(\pm 3days)

Atezolizumab patients will have immune monitoring samples on Days 1(\pm 24hrs), 43(\pm 3days) and 64 (\pm 3days).

Pembrolizumab patients will have immune monitoring samples on Days 1 (\pm 24hrs), 43(\pm 3days) and 64 (\pm 3days).

1.10.1.3 7.3 Determine the repertoire of humoral responses induced by immunotherapy and radiation

We will use seromics technology to evaluate the repertoire of antibody responses. Seromics is an antibody profiling method utilizing protein microarrays with the capacity to detect >8000 antigens induced by a vaccine. Assays will be performed as described previously.³⁷ Plasma/serum collected at the various time points will be plated onto ProtoArrays (v4.0; Invitrogen) and incubated with fluorescent antibodies. Arrays will be scanned at 10uM resolution using microarray scanner (Axon 4200AL with GenePix Pro Software; Molecular Devices) to detect fluorescence. We will look specifically at antibodies to neoepitopes, differentiation and cancer-testis antigens, in addition to p53, survivin etc.

1.10.1.4 7.4 Determine the induction and the quality of the T cell responses in patients

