The main immunological end-point will be the induction or boosting of treatment induced T cells (CD4+ and CD8+) and B cells for defined antigen approaches. In addition, the magnitude and duration of T and B cell responses will be examined. Treatment-induced responses will be calculated as the difference between the pre-treatment measurement and the measurement at the different time points at which blood was collected (time of evaluation) in the same patient. The percentage of patients with the induction of treatment-induced T and B cell responses will be reported.

1.11 8.0 Subject Selection Criteria

1.11.1.1 8.1 Inclusion Criteria

1. Ability to understand and the willingness to sign a written informed consent document;
2. Any prior therapy is permitted except prior therapy with PD1/PDL1 inhibitor.
3. Histologic diagnosis of metastatic renal cell carcinoma or urothelial cancer;
4. Patients must have at least 2 distinct measurable metastatic sites at least 1 cm or larger in their largest diameter per RECIST 1.1
5. Patients must have adequate organ and marrow function as defined by initial laboratory tests:
 - WBC $\geq 2000/uL$
 - ANC $\geq 1000/uL$
 - Platelets $\geq 50 \times 10^3/uL$
 - Hemoglobin $\geq 10.0 \text{ g/dL}$
 - Creatinine $\leq 3.0 \times \text{ULN}$
 - AST/ALT $\leq 2.5 \times \text{ULN}$
 - Bilirubin $\leq 3.0 \times \text{ULN}$, (except patients with Gilbert's Syndrome, who must have a total bilirubin less than 3.0 mg/dL);
6. At least 2 weeks since last chemotherapy and 4 weeks since last immunotherapy treatment.
7. At least 2 weeks since last radiation therapy.
8. Performance status ECOG 0-1
9. Men and women, ages > 18 years of age.
10. Life expectancy > 3 months
11. Stable brain metastases for at least 4 weeks and not steroid dependent
12. Women of childbearing potential (WOCBP) must be using an adequate method of contraception to avoid pregnancy throughout the study and for up to 8 weeks after the study in such a manner that the risk of pregnancy is minimized. Should a woman become pregnant or suspect she is pregnant while she is enrolled in this study, she should inform her treating physician immediately.

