1. Distribution of changes in T cells from baseline to response evaluation.
2. Association between abscopal responses and T cell changes from baseline. Changes from baseline in immune responses will be summarized over the time course of the study and post treatment using descriptive statistics and graphical displays. The patterns of changes in immune parameters will be examined using exploratory statistical approaches to assess the relationship of changes in individual parameters to clinical outcomes. Mixed effects regression models and general estimating equations will be used to compare the patterns of change in immune response over time in the two treatment groups.

Changes from pretreatment to follow up levels of immunologic parameters and other parameters described above in irradiated tumors (and non-irradiated tumors) will be compared between the two treatment groups using descriptive statistics and graphical displays.

All patients will be followed for progression-free survival and overall survival. Kaplan-Meier curves for progression-free survival and overall survival will be provided to summarize the results.

1.24.1.2 29.2 Interim Analyses

A futility analysis will be conducted after 50% of the total 18-week RECIST responses (estimated median time to response ~14 weeks) for final analysis have occurred (i.e., N/2 of N). No accrual suspension is required to conduct the futility analysis. If at this point the relative risk of no response in the immunotherapy arm over the immunotherapy plus radiation arm is 1.0 or less, the study will be stopped for futility.

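### Section 29.1 compares immune change between arms without saying how the pre-treatment value enters the model; stating baseline adjustment would be a free improvement

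*Combined protocol and SAP*

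**What the plan says.** Specific aim 3 in section 6.2 is a comparison of the randomised arms: "To compare the induction of effector T cell responses in patients with metastatic renal cell and urothelial cancer treated with either immunotherapy alone" or with radiation added. Section 7.6 defines the measure: "Treatment-induced responses will be calculated as the difference between the pre-treatment measurement and the measurement at the different time points". The only summary that 7.6 names is a proportion: "The percentage of patients with the induction of treatment-induced T and B cell responses will be reported".

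The between-arm methods are in section 29.1, in three places:

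- For blood parameters over time: "Mixed effects regression models and general estimating equations will be used to compare the patterns of change in immune response over time" between the two treatment groups. No covariates are listed.
- For parameters measured in tumours, changes "will be compared between the two treatment groups using descriptive statistics and graphical displays".
- For the distribution of T-cell changes from baseline, the text refers back to techniques like those just described. These include two-sample tests (t, Kruskal-Wallis, chi-square, Fisher) and descriptive summaries. Which of them is meant is unclear.

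A pre-treatment blood sample is planned for every patient (sections 7.2 and 12.1). Two later draws follow: Days 29 and 57 on nivolumab, Days 43 and 64 on atezolizumab or pembrolizumab. Nothing in 7.6 or 29.1 names the pre-treatment immune value as a covariate. For the time-to-event endpoints, by contrast, 29.1 does plan Cox regression with baseline characteristics.

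Section 7.1 gives the status of this work: "These immune analyses are considered exploratory and ancillary to the primary goals of the trial".

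**The concern.** A change score fixes the coefficient of the baseline value at 1. If the true regression slope of the post-treatment value on the pre-treatment value is not 1, the subtraction leaves avoidable variance in the arm contrast. Any chance difference between arms at baseline also carries into the estimated effect. A mixed model that includes baseline as an outcome and gives each arm its own baseline mean has the same weakness, because its arm-by-time contrast is the difference in changes.

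At stake is the precision of the trial's mechanistic comparison, immunotherapy alone against immunotherapy plus radiotherapy, with at most 56 patients per arm. Leaving the role of baseline open also leaves a modelling choice to be made after the data are seen.

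**Working it through.** **Inputs.** From the documents: 112 patients randomised 1:1, so 56 per arm (section 29.0), and one pre-treatment and two later blood draws (section 7.2). Not in the documents, and therefore assumed: the correlation ρ between pre- and post-treatment values, the ratio k of post- to pre-treatment SD, the test level, and the power of the unadjusted comparison.

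**The plan's own figure.** The only stated power is 90% for the primary response comparison (20% against 40%, one-sided alpha 20%). Exact enumeration of the one-sided Fisher test with 56 per arm gives 90.2%, so it reproduces. No power is stated for any immune endpoint, so no stated figure is in error here.

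**Step 1: variance per patient**, with pre-treatment SD set to 1.

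- Change score: 1 + k² − 2ρk
- Baseline-adjusted: k²(1 − ρ²)
- Difference: (1 − ρk)²

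The difference is never negative and is zero only when the slope ρk equals 1. Apart from the one degree of freedom spent on the slope, adjustment cannot be less precise. The variance ratio is R = k²(1 − ρ²)/(1 + k² − 2ρk). With k = 1 this reduces to (1 + ρ)/2.

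**Step 2: power.** Suppose the change score has 80% power. Adjusted power is Φ((z_α + z_0.80)/√R − z_α). At two-sided 5%, z_α + z_0.80 = 1.960 + 0.842 = 2.802. For ρ = 0.5 and k = 1: 2.802/√0.75 = 3.235; 3.235 − 1.960 = 1.275; Φ(1.275) = 89.9%.

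| ρ | k | Slope ρk | R | Adjusted power |
|---|---|---|---|---|
| 0.3 | 1 | 0.30 | 0.65 | 93.5% |
| 0.5 | 1 | 0.50 | 0.75 | 89.9% |
| 0.7 | 1 | 0.70 | 0.85 | 86.0% |
| 0.5 | 0.8 | 0.40 | 0.571 | 96.0% |
| 0.3 | 2 | 0.60 | 0.958 | 81.7% |
| 0.5 | 1.5 | 0.75 | 0.964 | 81.4% |
| 0.7 | 1.5 | 1.05 | 0.998 | 80.1% |
| 0.5 | 2 | 1.00 | 1.00 | 80.0% |

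At the one-sided 20% level that the plan uses for its primary test, with ρ = 0.5 and k = 1: (0.842 + 0.842)/√0.75 − 0.842 = 1.102, which gives 86.5%, a gain of 6.5 points.

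**Step 3: the mixed model.** Take three visits, compound symmetry, ρ = 0.5 and 56 per arm, and consider the variance of the arm effect at the last visit.

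- Separate baseline means per arm: 0.0357 = (2/56) × 1.00, the change-score variance.
- Common baseline mean: 0.0268 = (2/56) × 0.75, the adjusted variance.

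The same named method gives either result, depending on a choice that the plan does not state.

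**Step 4: chance imbalance.** Given an observed baseline difference D between arms, the change-score contrast is shifted by (ρk − 1)D. With 56 per arm, the standard error of D is √(2/56) = 0.189 SD. At ρ = 0.5 and k = 1, an imbalance of one standard error shifts the contrast by 0.5 × 0.189 = 0.094 SD. That is half the contrast's own standard error of √(2/56) × √1.00 = 0.189 SD.

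**The case against.** The strongest reply is that silence is being read as a decision. Section 7.6 defines a within-patient quantity and describes no test between arms. The between-arm method in 29.1 is mixed models and GEE, which can carry baseline adjustment without any change of method. A reader might infer that the plan commits to comparing raw changes without adjustment. The text does not say that. It neither specifies adjustment nor rules it out, and the wording on T-cell changes could mean two-sample tests or only descriptive summaries.

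A reader might also infer a definite loss, such as ten points of power. The documents do not support that either. It needs ρ = 0.5, equal SDs before and after treatment, and an 80% benchmark at two-sided 5%, and none of these is in the plan. Section 7.6 is about inducing or boosting responses, so a wider spread after treatment is plausible. At ρ = 0.5 with the post-treatment SD twice the baseline SD, the gain is zero.

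The arithmetic also concerns continuous measures. It does not cover the percentage of patients with an induced response or the descriptive tumour comparisons.

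All of this stands as a limit on size and wording. It does not remove the point: aim 3 compares arms, the pre-treatment value is collected, and the plan leaves open an analysis that can only match or fall short of the adjusted one.

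**Conclusion.** The point holds as a free improvement to an exploratory analysis. The plan defines immune response as a change and compares change between randomised arms without specifying how the pre-treatment value is used. The direction is certain: up to one degree of freedom, adjustment never loses precision, and it removes the effect of chance baseline imbalance.

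The size is not known. From an assumed 80% power at two-sided 5%, the gain is 13.5, 9.9 and 6.0 points at ρ of 0.3, 0.5 and 0.7 with equal SDs. It is larger if the post-treatment SD is smaller than the baseline SD, and nil when the slope is 1. The primary best overall response result, its sample size and its stated power are untouched.

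**What to change.** In section 29.1, keep change scores for description. For between-arm comparisons of continuous blood immune parameters, state one of two equivalent forms:

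- model the post-treatment values, log-transformed where skewed, with the Day 1 pre-treatment value as a covariate; or
- use the planned mixed model with baseline among the outcomes and a common baseline mean for both arms.

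For GEE, name the covariate form, because the common-mean form gains precision only when the within-patient correlation is modelled. Report the adjusted arm difference at each post-treatment draw, noting that the draw days differ by drug. The covariate should be the sample that section 12.1 requires before both radiation and drug; the calendar footnotes say only that it precedes infusion.

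The cost is a sentence or two of text. No new data, visits or patients are needed.
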